5. SUBJECT SELECTION

5.1. STUDY POPULATION

Up to 200 patients will be enrolled in the study (male and female).

5.2. INCLUSION CRITERIA

All patients must comply with the following Inclusion Criteria:

- 1. Informed consent form (ICF) signed by the subject or legally acceptable representative. If a legally acceptable representative signs the ICF, a notation of capacity of the subject must be noted.
- 2. Patient has a caregiver or legal representative responsible for administering the drug and recording the time.
- 3. Ages \geq 50 and \leq 85 years

- 4. Clinical diagnosis of dementia due to possible or probable AD consistent with criteria established by a workgroup of the National Institute on Aging and the Alzheimer's Disease Association.
- 5. If female, postmenopausal for at least 1 year
- 6. Patient living at home, senior residential setting, or an institutional setting without the need for continuous (i.e. 24-h) nursing care
- 7. General health status acceptable for participation in the study
- 8. Fluency (oral and written) in English or Spanish
- 9. If receiving memantine, rivastigmine, galantamine or an AChEI, receiving a stable dose for at least 3 months (90 days) before screening. If receiving donepezil, receiving any dose lower than 23 mg once daily. Multiple medications are allowed.
- 10. The patient is a non-smoker for at least 3 years.
- 11. The patient or legal representative must agree to comply with the drawing of blood samples for the PK assessments, laboratory assessments and SavaDx.
- 12. MMSE-2 score \geq 16 and \leq 26 at screening, OR if > 26, must have evidence of AD pathology such as a prior CSF total tau/A β_{42} ratio \geq 0.28, an amyloid positive PET scan or hippocampal volume loss consistent with AD.

5.3. EXCLUSION CRITERIA

Patients meeting any of the following Exclusion Criteria will be excluded from the study:

- 1. Anything that in the opinion of the Investigator would preclude participation in a 2year study.
- 2. BMI < 18.5
- 3. Positive urine drug screen.
- 4. Positive HIV, HCV or HbsAg screen.
- 5. Suicidality on C-SSRS
- 6. Exposure to an experimental drug other than simufilam, experimental biologic or experimental medical device within 3 months before screening
- 7. A medical condition that would interfere with a lumbar puncture
- 8. Residence in a skilled nursing facility and requiring 24 h care.
- 9. Clinically significant laboratory test results

- 10. Clinically significant untreated hypothyroidism (if treated, thyroid-stimulating hormone level and thyroid supplementation dose must be stable for at least 6 months before screening)
- 11. Insufficiently controlled diabetes mellitus, including requiring insulin or metformin >1000 mg/day.
- Renal insufficiency (serum creatinine > ULN and clinically significant in the opinion of PI and/or Sponsor OR eGFR <60 ml/min/m² as estimated by either the MDRD or CKD-EPI equation)
- 13. Malignant tumor within 3 years before screening (except squamous and basal cell carcinoma or cervical carcinoma in situ or localized prostate cancer or localized stage 1 bladder cancer)
- 14. History of ischemic colitis or ischemic enterocolitis
- 15. Unstable medical condition that is clinically significant in the judgment of the investigator
- 16. Alanine transaminase (ALT) or aspartate transaminase (AST) > ULN or total bilirubin > ULN and clinically significant in the opinion of PI and/or Sponsor.
- 17. History of myocardial infarction or unstable angina within 6 months before screening
- 18. History of more than 1 myocardial infarction within 5 years before screening
- 19. Clinically significant cardiac arrhythmia (including atrial fibrillation), cardiomyopathy, or cardiac conduction defect (patients with a pacemaker are acceptable)
- 20. Symptomatic hypotension, or uncontrolled hypertension
- 21. Clinically significant abnormality on screening electrocardiogram (ECG), including but not necessarily limited to a confirmed QTc (Fridericia correction method) value \geq 450 msec for males or \geq 470 msec for females.
- 22. Stroke within 18 months before screening, or history of a stroke concomitant with onset of dementia
- 23. History of brain tumor or other clinically significant space-occupying lesion on CT or MRI
- 24. Head trauma with clinically significant loss of consciousness within 12 months before screening or concurrent with the onset of dementia
- 25. Onset of dementia secondary to cardiac arrest, surgery with general anesthesia, or resuscitation
- 26. Specific degenerative CNS disease diagnosis other than AD (e.g., Huntington's disease, Creutzfeld-Jacob disease, Down's syndrome, Frontotemporal Dementia, Parkinson's disease)

- 27. Wernicke's encephalopathy
- 28. Active acute or chronic CNS infection
- 29. Donepezil 23 mg or greater QD currently or within 3 months prior to enrollment
- 30. Discontinued AChEI < 30 days prior to enrollment
- 31. Antipsychotics; low doses are allowed only if given for sleep disturbances, agitation and/or aggression, and only if the subject has received a stable dose for at least 3 months before enrollment
- 32. Tricyclic antidepressants and monoamine oxidase inhibitors; all other antidepressants are allowed only if the subject has received a stable dose for at least 3 months before enrollment
- 33. Anxiolytics or sedative-hypnotics, including barbiturates (unless given in low doses for benign tremor); low doses of benzodiazepines and zolpidem are allowed only if given for insomnia/sleep disturbance, and only if the subject has received a stable dose for at least 3 months before enrollment
- 34. Immunosuppressants, including systemic corticosteroids, if taken in clinically immunosuppressive doses (Steroid use for allergy or other inflammation is permitted.)
- 35. Antiepileptic medications if taken for control of seizures
- 36. Chronic intake of opioid-containing analgesics
- 37. Sedating H1 antihistamines
- 38. Nicotine therapy (all dosage forms including a patch), varenicline (Chantix), or similar therapeutic agent within 30 days before screening
- 39. Clinically significant illness within 30 days of enrollment
- 40. History of significant neurological, hepatic, renal, endocrine, cardiovascular, gastrointestinal, pulmonary, or metabolic disease
- 41. Loss of a significant volume of blood (> 450 mL) within 4 weeks prior to enrollment
- 42. COVID-19 infection within 3 months of screening

6. STUDYDRUG

6.1. STUDY DRUG PHYSICAL DESCRIPTION AND PREPARATION

Investigational simufilam and placebo will be supplied by Cassava Sciences as coated tablets in 70- or 200-count bottles. Several days of extra tablets are included in each bottle to allow flexibility of scheduling visits.

All remaining study drug will be returned to the sponsor or designee.

6.1.1. Storage

Bottles of study drug tablets should be stored at controlled room temperature, 20- 25° C (68-77° F) and protected from light and moisture.

6.1.2. Drug Accountability

The Investigator will be responsible for monitoring the receipt, storage, dispensing and accounting of all study medications according to site SOPs. All invoices of study medication shipments must be retained in the site study file. Accurate, original site records must be maintained of drug inventory and dispensing. All records must be made available to the sponsor (or designee) and appropriate regulatory agencies upon request.

6.2. ADMINISTRATION AND DOSING REGIMEN

Patients will receive 100 mg simufilam b.i.d. during the open-label portions of the study and either 100 mg simufilam or matching placebo during the randomized withdrawal portion of the study. Simufilam or placebo tablets should be at least 1 h before or after a meal.

6.3. CONCOMITANT MEDICATIONS

Use of prescription or non-prescription medications will be recorded during the study. Chronic medications must be stable for 3 months at entry.

7. STUDY PROCEDURES

Appendix A presents the Schedule of Activities.

Prior to any study-related activities, the Informed Consent Form (ICF) must be signed and dated by the patient or legal representative. The format and content of the ICF must be agreed upon by the Principal Investigator(s), the appropriate IRB and the Sponsor (or designee). The signed and dated ICF must be retained by the Investigator in the subject's file.

7.1. STOPPING CRITERIA

Liver chemistry threshold stopping criteria have been designed to assure patient safety and to evaluate liver event etiology during administration of Study Drug. Administration of Study Drug will be discontinued if any of the following liver chemistry stopping criteria occurs:

- ALT or $AST \ge 3 \times ULN$.
- ALT or AST \geq 2.5 x ULN and total bilirubin \geq 2 x ULN.
- ALT or $AST \ge 2 \times ULN$ if associated with appearance or worsening of a rash or hepatitis symptoms (fatigue, nausea, vomiting, right upper quadrant pain or tenderness, fever, rash or eosinophilia).
- ALT or GGT \geq 2.5 x ULN that persists for \geq 4 weeks.

In the event of discontinuation due to liver abnormalities, the patient will be appropriately investigated to determine the potential cause and referred to a physician experienced in the treatment of hepatic disorders.

An additional stopping criterion will be bodyweight loss of ≥ 2 kg resulting in a BMI < 18.5.

7.2. EVALUATIONS BY VISIT

7.2.1. Screening Visit 1 (Days -29 to 0)

Patients who completed PTI-125-02 < 60 days of study start will not be rescreened but will sign the ICF on Day 1 or earlier for this open-label extension.

For all other patients, the following will be completed in the screening visit:

- Informed Consent
- Review of Inclusion and Exclusion Criteria
- Medical history
- Review of concomitant medications
- Confirmation that the patient is either fully vaccinated for the COVID-19 virus at least 2 weeks prior to first dose of simufilam, or a positive serology test for the COVID-19 virus with no current symptoms
- If needed, CT scan to confirm I/E criteria, per investigator judgement
- MMSE-2 evaluation (prior patients do not need to meet 16 to 26 range)
- Columbia Suicide Severity Rating Scale (C-SSRS)
- Physical examination, including measurement of vital signs (blood pressure, temperature, pulse and respiratory rate), height, weight
- A 12-lead ECG (5-min supine)
- Laboratory assessments, including serum chemistry, hematology, urinalysis, and screens for HCV, HIV and HBsAg.
- Urine drug screen.

7.2.2. Screening Visit 2 (Days -28 to 0)

This CSF draw is **required for all NEW patients** meeting Screening Visit 1 criteria who do not have a prior positive amyloid PET scan or MRI showing hippocampal volume loss OR prior CSF biomarkers confirming AD. If Screening Visit 2 and Study Day 1 visit are combined, the CSF sample collection will occur 1-3 h after dosing and after the MMSE-2, ADAS-Cog11, NPI and GDS testing has been completed.

- CSF sample collection (5 mL)
- CSF samples should be held at the study site frozen at -70°C, pending shipping instructions from the Sponsor.

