4. SUMMARY OF STUDY DESIGN

The first 12 months is an open-label treatment of simufilam 100 mg b.i.d. for patients who completed prior Phase 2 studies PTI-125-02 and PTI-125-03. New patients are included so that up to 200 patients are enrolled in this study. Month 12 to Month 18 is a randomized withdrawal phase; patients will be randomized to continue taking simufilam 100 mg b.i.d. or matching placebo. Month 18 to Month 24 will be an additional 6 months of open-label simufilam 100 mg b.i.d. Simufilam and placebo will be administered as coated oral tablets. Patients who were enrolled prior to this amendment can continue upon reconsenting to the randomized withdrawal and final 6-month open-label portion.

All patients will provide consent to enroll into this study. Unless patients have a prior positive amyloid PET scan, MRI showing hippocampal volume loss or other prior evidence of AD, patients will undergo a CSF draw (if all other screening criteria are met) to confirm a total tau/A β_{42} ratio ≥ 0.28 .

Patients will report to the clinic in the morning of Day 1. Prior to dosing, patients will complete the following baseline measures: ECG, vital signs, clinical labs, urinalysis, listen to heart and lungs, ADAS-Cog11, neuropsychiatric inventory (NPI), geriatric depression scale (GDS), and the C-SSRS. A blood sample will be collected for plasma-based biomarkers and genetic testing.

Patients will return to the clinic every month through Month 3 and every 1.5 months through Month 12. Visits on Months 4.5, 7.5 and 10.5 will include vital signs, listening to heart and lungs, AE monitoring, C-SSRS, and drug dispensation and accountability only and may be conducted by telemedicine, based on the judgement of the Investigator. After Month 12, visits will be on Months 13, 15, 18, 21 and 24. Patients completing Month 12 prior to availability of drug supply for the randomized withdrawal phase will continue with active treatment until drug supply is ready and therefore will have an additional "Withdrawal Day 1" visit before resuming with the Month 13 visit one month later.

PK blood samples will be obtained in the morning before dosing at return visits on Months 15 and 18.

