7.2.3. Study Day 1 (Dosing Initiation)

Patients will come to the clinic in the morning. Prior to dosing, the following assessments will be conducted:

- Confirmation of Inclusion/Exclusion Criteria
- Review of concomitant medications
- Vital signs (blood pressure, temperature, pulse and respiratory rate), and weight
- Listen to heart and lungs
- ADAS-Cog11, NPI, GDS testing and C-SSRS Since Last Visit version. If the C-SSRS indicates imminent risk for suicidality, defined as the patient positively endorsing questions 4 or 5 of the suicidal ideation section or any suicidal behavior questions, discontinue study drug and refer for appropriate care.
- Blood sample collection for clinical laboratory tests
- Plasma sample collection for SavaDx and other plasma biomarkers.
- ECG

Patients will be administered 100 mg simufilam b.i.d. 1-2 h before or after a meal.

After dose on Study Day 1, the following assessments will be conducted:

- Vital signs (blood pressure, temperature, pulse and respiratory rate) at approximately 30 min, and 1 and 2 h post-dose.
- Adverse event monitoring

Clinic personnel will monitor the patients for AEs until discharge from the clinic. Upon investigator judgment, patients will be discharged with their supply of study drug until the next visit. They will be instructed to take study drug twice daily, at least 1-2 h before or after a meal. A dose can be up to 4 h late, but if a dose is missed, the next dose should NOT be doubled.

All follow-up visits can be +/- five (5) days for flexibility. For all follow-up visits except Months 4.5, 7.5 and 10.5, patients will come to the clinic in the morning and will be instructed NOT to take their morning dose prior to coming to the clinic.

7.2.4. Follow-up Visits on Months 1, 3, 9, 13, 15, 21

Patients will return to clinic in the morning before taking their morning dose.

Within 30 min prior to dosing, the following assessments will be conducted:

- Blood sample collection for PK assessment (for Cmin Month 15 only)
- Clinical laboratory tests (blood and urine) (All visits except Month 13)
- **Plasma** sample collection (from 8 mL whole blood) for SavaDx and other plasma biomarkers (All visits **except Months 1 and 13**)

After dose, the following assessments will be conducted:

- Vital signs (blood pressure, temperature, pulse and respiratory rate), and weight
- Listen to heart and lungs
- ECG (Month 1 only)
- Adverse event monitoring

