5.1 Efficacy Analysis

General Considerations

Efficacy and biomarker analyses will be based on the FAS analysis set. No adjustments for multiple comparisons will be made. Baseline values for each endpoint are defined as the last non-missing value taken on or prior to Day 1.

Unless otherwise specified, for continuous endpoints that are scheduled to be assessed at only 1 post-baseline visit (MMSE-2), mean changes from baseline will be analyzed using ANCOVA. The analysis will include the categorical, fixed effect of enrollment group (mild vs. moderate AD) along with the continuous, fixed covariate of baseline value of the endpoint being analyzed (baseline). Significance tests comparing endpoint LSMEANS by enrollment group (mild vs. moderate) will be based on least-squares means. Significance of within-group mean changes from baseline will also be reported.

Biomarker exploratory endpoints

Biomarker endpoints to be analyzed may include: 1) CSF Aβ42, 2) CSF tau 3) CSF p- tau181, 4)Version 3.0CONFIDENTIAL, MATERIAL NON-PUBLIC INFORMATIONPage 15 of 19

CSF neurofilament light chain, 5) CSF neurogranin, 6) CSF sTREM2, 7) CSF YKL40 8) CSF HMGB1 9) plasma neurofilament light chain, 10) plasma GFAP, or other non-safety related exploratory biomarkers of disease.

Plasma biomarker data may be analyzed with the MMRM model described above. CSF biomarker data may be analyzed by descriptive statistics.

Note: All biomarker assessments in this study are exploratory endpoints that are not patient safety related; are 'Research Use Only' products; and, hence, are not intended to be compliant with FDA's Quality System Regulation (QSR) or ISO equivalent.

Clinical endpoints

The ADAS-Cog11 will be analyzed using the MMRM model described above. MMSE will be analyzed by ANCOVA.

6 Analysis of Randomized Withdrawal Phase

The following efficacy analyses will be applied to data from the RW phase, which begins after the month 12 assessment and continues through month 18.

These analyses are similar to the analyses from the Open-Label phase except:

- 1) treatment group replaces enrollment group in the analysis models
- 2) baseline value is defined as the last non-missing value at or prior to month 12; or, for patients who were maintained on open-label treatment beyond month 12, baseline is defined as the last non-missing value at or prior to the withdrawal day 1 assessment.

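### When Screening Visit 2 is merged with Day 1, the confirmatory CSF sample follows the first dose, and the SAP accepts it as a CSF baseline that is not drug-free

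*Protocol*

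**What the plan says.** Protocol Section 4 presents the CSF draw as part of screening. Unless there is earlier evidence of AD, "patients will undergo a CSF draw (if all other screening criteria are met) to confirm a total tau" to Aβ42 ratio of at least 0.28.

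Protocol Section 7.2.2 requires the draw of new patients "who do not have a prior positive amyloid PET scan or MRI showing hippocampal volume loss OR prior CSF biomarkers confirming AD". The visit window in its heading is Days -28 to 0. The same section allows the visit to be merged with Day 1: "If Screening Visit 2 and Study Day 1 visit are combined, the CSF sample collection will occur 1-3 h after dosing", with the cognitive and behavioural scales done before the draw. On handling it says: "CSF samples should be held at the study site frozen at -70°C, pending shipping instructions from the Sponsor".

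Protocol Section 7.2.3 covers Day 1, the start of dosing. Its list of assessments before dosing begins with "Confirmation of Inclusion/Exclusion Criteria". It lists no CSF draw, before or after the dose. Appendix A likewise marks the CSF draw under Screen Visit 2 and leaves Day 1 blank. An Appendix A footnote calls this sample the baseline CSF draw.

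SAP Section 5.1 sets the baseline for the open-label phase: "Baseline values for each endpoint are defined as the last non-missing value taken on or prior to Day 1". SAP Section 1.3 plans the CSF change from baseline to Month 6 or Month 12, and Protocol Section 10.3 plans a paired t test on the same contrast.

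**The concern.** Two separate things depend on when this sample is taken.

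The first is the confirmation of disease. A sample drawn after the dose cannot inform the decision to give that dose. Yet Section 4 describes the draw as a screening confirmation, and Section 7.2.3 has the entry criteria confirmed before dosing.

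The second is the CSF baseline. The SAP rule goes by calendar day, so a sample taken a few hours after the first dose qualifies. CSF change from baseline would then combine patients whose baseline is drug-free with patients whose baseline is not, and nothing in the SAP would reveal it. Plasma is handled differently: Protocol Section 4 and SAP Section 2.2 both place the Day 1 plasma sample before dosing.

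**Working it through.** The plan gives no figure on this point, so there is nothing to reproduce. The check is a reading of the sections against each other.

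1. **Is the Day 1 dose the first dose?** Yes. Section 7.2.2 requires the draw only of new patients, and Section 7.2.3 is where their dosing starts.

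2. **Does the merged visit fit the rest of the protocol?** No, on four counts. Section 4 places the draw within screening. Section 7.2.3 confirms entry criteria before the dose and schedules no CSF draw that day. The Screening Visit 2 window ends at Day 0. Appendix A shows no CSF draw on Day 1.

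3. **Can the ratio be known at first dose?** Not in a merged visit, because the sample does not yet exist. With separate visits it may also be unknown: samples stay frozen on site until the sponsor asks for them, and no section requires the result before Day 1. Merging the visits makes prior knowledge impossible, but separating them does not secure it.

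4. **Is the ratio a formal entry criterion?** Sections 4 and 5.2 differ. Inclusion criterion 12 asks for evidence of pathology only when MMSE-2 exceeds 26. For scores of 16 to 26 it sets no CSF threshold, and SAP Section 2.3 repeats this. The documents also do not say how a dosed patient whose ratio later proves below 0.28 is to be treated in the analysis. The Per Protocol set in SAP Section 3.2 removes major violations of entry criteria, but under Section 5.2 such a patient with a score of 16 to 26 is not clearly a violator.

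5. **Does the SAP accept the post-dose sample as baseline?** Yes. The rule includes Day 1 and has no pre-dose condition.

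6. **Which analyses are affected?** The open-label CSF change to Month 6 or 12, planned around 50 patients (25 at each time). The randomized-withdrawal phase takes its baseline at Month 12 or Withdrawal Day 1 (SAP Section 6), so its ADAS-Cog11 comparison is untouched.

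7. **What could the effect on the CSF mean be?** Let D be the mean change from a drug-free baseline, c the share of CSF patients with a merged visit, and f the fraction of D already present at the post-dose draw.
   - Separate visits: observed change = D.
   - Merged visits: observed change = D - fD = (1 - f)D.
   - Pooled: (1 - c)D + c(1 - f)D = (1 - cf)D.

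   The documents give neither c nor f. If either is zero, the shift is zero. Purely as an assumed upper illustration, c = 0.50 and f = 0.50 give cf = 0.25, a 25% shrinkage. If a first dose moved the marker the opposite way (f negative), the change would be inflated instead. The formula shows only what would have to be known.

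**The case against.** The case on the other side is substantial.

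- **Eligibility under Section 5.2 can be settled before dosing.** For MMSE-2 of 16 to 26 the criteria require a clinical diagnosis of possible or probable AD, not a CSF ratio. A reader might infer that merged-visit patients are dosed with their eligibility unknown. The documents do not support that in general: what is outstanding is the Section 4 confirmation. This stands, and it limits the point.
- **The ratio may be missing with separate visits too.** This stands. The order of draw and dose is only part of the problem.
- **Follow-up CSF is also drawn after dosing**, at 1-3 h in Section 7.2.8 (Month 12) and after the dose in Section 7.2.7 (Month 6). For merged-visit patients, baseline and follow-up are therefore both post-dose samples. This is correct, but patients sampled on Days -28 to 0 have a drug-free baseline, so the pooled summary still mixes two contrasts.
- **The sentence may be a drafting carry-over**, since it closely resembles the follow-up CSF sentence in Section 7.2.8. That is possible, but it is still an instruction to sites as it stands.
- **The endpoints are exploratory.** SAP Sections 1.3 and 5.1 call the biomarkers exploratory, and Section 5.1 says CSF data may be summarised descriptively. This stands and keeps the consequence small. A descriptive change still needs a baseline with one meaning.

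**Conclusion.** The point holds for a limited group: new patients without earlier PET, MRI or CSF evidence whose Screening Visit 2 was merged with Day 1. For them, Section 7.2.2 conflicts with Sections 4 and 7.2.3, its own visit window and Appendix A. The Section 4 confirmation cannot be available at first dose, and the SAP takes a post-dose sample as CSF baseline.

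The documents do not give the number of such patients, which may be zero. They also do not allow the size or direction of any bias to be derived. A reader might infer a definite attenuation because the protocol reports CSF changes by Day 28 in its Phase 2 studies (Sections 2.3.2 and 2.3.3). Those results follow repeated dosing and say nothing about CSF 1-3 h after a first dose, so no percentage can be claimed.

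The consequence is confined to the exploratory open-label CSF summaries. The safety analyses and the randomized-withdrawal ADAS-Cog11 estimand do not use this baseline. The point is worth correcting mainly because the SAP part is cheap.

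**What to change.** **Protocol.** Reconcile Sections 4, 5.2, 7.2.2 and 7.2.3 and Appendix A on the order of CSF confirmation and first dose, and on whether the ratio is an entry criterion. Which order is right is not a question for this review. SAP Section 2.5 reports 220 patients already enrolled, so this can clarify the record but cannot change what was done.

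**SAP.** Define CSF baseline as the last non-missing value before the first dose. Identify Day 1 samples drawn after dosing, then either exclude them from CSF change-from-baseline summaries or show them separately, and report how many there were. Dose and draw times will have to be checked in source records: Sections 7.2.7 and 7.2.8 ask for time post-dose to be recorded at Months 6 and 12, but Section 7.2.2 makes no such request for the merged visit.

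**Cost.** A protocol clarification, one added SAP sentence, a source-record check, and a somewhat smaller CSF change sample if post-dose baselines are excluded. If no visits were merged, nothing is lost and the CSR can say so.
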